#### 3.3 Study Objectives

#### 3.3.1 Primary Objectives

- 1) Determine the effect of repeat dosing of LACTIN-V (2 x 10^9 cfu/dose) on genital tract inflammation in young South African women at risk of HIV.
- 2) Determine the ability of LACTIN-V to promote a *Lactobacillus*-dominant vaginal microbiota in young South African women at risk of HIV.
- Determine the safety and acceptability of LACTIN-V in a population of young South African women at risk for HIV.

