#### 4:

The proportion of subjects with cervicotypes I-IV compared by study arm.

Primary / Secondary Outcome Safety Measures for Objective 3 (safety and acceptability)

Safety of LACTIN-V and the applicator will be measured by:

The proportion of participants reporting product-related AEs and SAEs through the final visit that are likely related to use of study product compared by study arm, in particular Grade 3 AEs and SAEs.

Acceptability of LACTIN-V and the applicator will be measured by standardized questionnaire about acceptability of the study product and participants' stated willingness to use this type of product in the future, in each study arm.

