# 11.2 Study Objectives and Outcome Measures

As described in section 3.2 and 3.3, the primary study objectives are to compare LACTIN-V with placebo following a 7-day treatment course with Metronidazole with respect to safety and impact on the vaginal microbiome, specifically *lactobacillus* growth and decrease in pro-inflammatory cytokines and HIV target cells.

In Objective 1, the outcomes of interest will be:

(1) a decrease in genital tract inflammation from baseline (the FRESH Study Visit before enrollment) to Day 36 Follow-Up Visit, as defined by a  $\geq$ 1 Log10 decrease in the concentration of cytokines that have been associated with an increased risk for HIV infection., and

(2) the change in the concentration of cytokines at the Final Visit on Day 64 (4 weeks after dosing phase completed) compared to baseline, number of endocervical CD4+ HIV target cells at Day 36 Follow-Up and Day 64 Final Visits compared to baseline, and in vitro anti-HIV activity of cervicovaginal lavage at Day 36 Follow-Up and Day 64 Final Visits. We will compare each outcome by study arm.

In Objective 2, the outcomes of interest will be:

(1) the presence of *Lactobacillus*-dominant vaginal microbial cervicotypes at the Day 36 Follow-Up Visit, and following the post-dosing phase at the Day 64 Final Visit in the LACTIN-V arm; and

(2) the comparison of *L. crispatus* vs. *L. iners* prevalence between treatment groups, quantity of vaginal *L. crispatus*, presence of the specific CTV-05 *L. crispatus* strain, persistence of colonization after stopping therapy, effect of sex and/or vaginal hygiene practices on colonization by lactobacilli, and stability of vaginal microbial communities over time in the treatment vs. placebo arms.

In Objective 3, the outcomes of interest will be:

- (1) the proportion of treatment related adverse events study arm, in particular Grade 3 AEs; and
- (2) the proportion of participants finding the product acceptable and are willing to use it Page 64 of 124

should it become commercially available, as measured in a standardized acceptability questionnaire.

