# 11.3 Sample Size Considerations

The study will accrue a total of 60 randomized subjects (n=20 for the placebo arm A and n=40 for the LACTIN-V arm B). The accrual for this study is expected to be completed within 75 weeks (18 months) with projected accrual rate of 3 subjects per month. Each subject will be followed up for 64 days.

The primary endpoint upon which the sample size calculation was based is the proportion of subjects with a  $\geq 1 \text{ Log}_{10}$  decrease in at least 3 of 9 proinflammatory cytokines in CVL specimens on the Day 36 Visit, i.e. at the completion of the LACTIN-V/Placebo dosing phase. The proportion of women with decreased inflammation will be compared between the two study arms. This endpoint is adapted from the CAPRISA 004 study which demonstrated that women with the highest levels of at least 3 of 9 proinflammatory cytokines in CVL specimens had an increased risk of HIV acquisition. Our adaptation of the CAPRISA 004 analysis is that we will define "decreased inflammation" as a  $\geq 1 \text{ Log}_{10}$ decrease in the concentration of at least 3 of the same 9 proinflammatory cytokines. Based on our prior data, we assume that no more than 10% of placebo-treated women will achieve a decrease in  $\geq 3$  of the 9 proinflammatory genital tract cytokines. Moreover, we hypothesize that at least half of the participants in the treatment arm will achieve a decrease  $\geq 1 \log_{10}$  in  $\geq 3$  of the 9 proinflammatory genital tract cytokines. With the targeted sample size of 60 randomized women (1/3 in placebo arm & 2/3 in the LACTIN-V arm; there will be more than 88% power to detect a 40% absolute difference (10% vs. 50%) in the proportion of women with decreased inflammation between the two treatment arms. This power calculation was based on simulation study using 10,000 Monte Carlo samples and two-sided Fisher's exact test with type 1 error rate of 5%.

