## 11.4 Safety Analysis

This study will be monitored for safety and to determine if any of the safety halting rules described in detail in Section 9.5 are met (one or more treatment-related SAE, two or more treatment-related vaginal ulceration, two or more treatment-related severe Grade 3 systemic adverse events). Thus, all patients will be evaluated for toxicity. The DSMB will review interim analyses comparing product-related AEs between the two treatment arms will be performed after half of the 60 participants complete the Follow-Up Study Visit 11, and then annually. Reports of these analyses will be sent to the Principal Investigator or Senior Investigators at the participating institutions.

The table below gives the probability of observing at least one incidence of AE together with the corresponding true AE rate for a total of 60 participants.

True AE rate:	0.5%	1%	2%	5%
P [AE>1]:	0.26	0.45	0.70	0.95

For example, the probability of observing at least one incidence of AE with true rate of 5% is 0.95.

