Sparse clustering, where clustering and feature selection are integrated, will be used to identify study subjects with similar microbial profiles. Sparse clustering has a number of advantages. If the underlying groups differ only in terms of some of the features, then it might result in more accurate identification of these groups than standard clustering. It also yields interpretable results, since one can determine precisely which features are responsible for the observed differences between the groups or clusters. Similarly, Sparse Principal Component analysis will be used to group a set of highly correlated microbial reads to uncorrelated summary variables. As in Objective 1, adjustment for multiple testing will be made using less conservative multiple testing correction methods (e.g., Benjamini-Hochberg).

Solicited AEs will be analyzed by taking the most severe response over the Day 64 followup period. The analyses of AEs and SAEs is mainly descriptive. Descriptive measures (frequency and percent) will be used to summarize the proportion of participants with product-related AEs (Grade 0, Grade 1, Grade 2, and Grade 3) in each treatment arm. Confidence intervals for AEs rates will be estimated using methods for exact binomial confidence intervals. Fisher's exact test will be used to compare rates of AEs between the two treatment arms. Multivariate analyses using logistic regression models will be used to compare AEs rates between the two arms while adjusting for the effect of other covariates.

Unsolicited AEs will be coded by MedDRA® for preferred term and system organ class. The proportion of participants and exact 95% confidence intervals of AEs in aggregate, as well as by MedDRA® categories, will be computed. The number of SAEs will be reported by a detailed listing showing the type, MedDRA® coding, relevant dates (treatment dosing dates and AE onset and resolution dates), severity, relatedness, and outcome for each event.

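### Does the section 11.4 adverse-event detection table overstate what the trial can show for the 40 LACTIN-V women?

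*Combined protocol and SAP*

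**What the plan says.** The third primary objective in section 3.3.1 is to "Determine the safety and acceptability of LACTIN-V in a population of young South African women at risk for HIV". The matching safety outcome in section 3.4.1 is AEs and SAEs "likely related to use of study product compared by study arm", and section 11.2 restates it as "the proportion of treatment related adverse events study arm, in particular Grade 3 AEs". Section 11.3 fixes the arm sizes at 20 placebo and "n=40 for the LACTIN-V arm B".

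Section 11.4 recalls the halting rules, says that every participant is assessed for toxicity, and has the DSMB review "interim analyses comparing product-related AEs between the two treatment arms". It then gives one detection table, presented "together with the corresponding true AE rate for a total of 60 participants", with probabilities 0.26, 0.45, 0.70 and 0.95 at true rates of 0.5%, 1%, 2% and 5%. The example sentence under the table reads "the probability of observing at least one incidence of AE with true rate of 5% is 0.95".

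Section 11.5 treats AE data as largely descriptive, with percentages by arm and Fisher's exact test between arms. On precision it says "Confidence intervals for AEs rates will be estimated using methods for exact binomial confidence intervals".

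**The concern.** The table is the plan's only statement of which AE rates the trial is likely to reveal, and it is built on 60 women when the product under test goes to 40. An event caused by the bacterial strain itself cannot come from a placebo made without that strain (section 6.1), so for such an event the 20 placebo women add nothing. The example sentence repeats neither the 60 nor any condition on the placebo rate. It also stands close to halting rules for treatment-related events and a between-arm comparison of product-related AEs. A DSMB or ethics reader could therefore take 0.95 as the chance of seeing a 5% LACTIN-V event.

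At stake would be a safety justification that looks stronger than it is: a 13% chance of missing a 5% event among LACTIN-V users, where the reader believes it is 5%.

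**Working it through.** **Inputs.** Pooled n = 60 and the four true rates come from section 11.4; arm sizes of 40 and 20 come from section 11.3. All women are taken as evaluable, and events in different women as independent.

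**Step 1: reproduce the plan's figures, then apply the same formula to 40 women.** P(at least one) = 1 − (1 − p)^n.

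| True rate p | Table in 11.4 | n = 60 | n = 40 |
|---|---|---|---|
| 0.5% | 0.26 | 0.2597 | 0.1817 |
| 1% | 0.45 | 0.4528 | 0.3310 |
| 2% | 0.70 | 0.7024 | 0.5543 |
| 5% | 0.95 | 0.9539 | 0.8715 |

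All four printed values reproduce with n = 60. The row label reads as strictly more than one event. Taken literally, that would give 0.0365, 0.1212, 0.3381 and 0.8084, so the text's *at least one* is what was computed and the label is a clerical slip or a PDF-reading artefact.

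**Step 2: the rate detectable with 95% probability.** Solve 1 − (1 − p)^n = 0.95, so p = 1 − 0.05^(1/n).

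- n = 60: 4.9%
- n = 40: 7.2%

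**Step 3: does the pooled row need equal rates in the two arms?** Let p be the LACTIN-V rate and q the placebo rate. Trial-wide, P = 1 − (1 − p)^40 × (1 − q)^20. The p, q pairs below are assumed for illustration.

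| p | q | Average over 60 women | P |
|---|---|---|---|
| 5% | 5% | 5% | 0.9539 |
| 6% | 3% | (40 × 6% + 20 × 3%)/60 = 5% | 0.9542 |
| 7.5% | 0% | (40 × 7.5%)/60 = 5% | 0.9558 |
| 5% | 0% | (40 × 5%)/60 = 3.3% | 0.8715 |

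The 0.95 holds whenever the average over the 60 women is about 5%, however it is split. The last line gives 0.87 because the average is then 3.3%, and the pooled formula at that average gives almost the same answer: 1 − (1 − 0.0333)^60 = 0.869. The table still applies; the reader has to enter it at the average rate.

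**Step 4: what would be inferred after the trial.** With zero events, the exact two-sided 95% upper limit is 1 − 0.025^(1/n): 8.8% for 0 of 40 and 6.0% for 0 of 60. Section 11.5 quotes neither limit, so neither contradicts a planned figure.

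**Step 5: what depends on the table.**

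- The sample size in section 11.3 rests on the cytokine endpoint.
- The halting rules in section 9.5 are counts of participants with treatment-related events, and no arm is named.
- The AE analyses in section 11.5 use the observed counts.

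None of these takes a number from the table.

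**The case for a change.** The strongest case for a change is that the figure matching the objective is the one left out. The objective concerns LACTIN-V, the outcome is compared by arm, and a product-specific event at 5% is seen with probability 0.87 whether one looks at the LACTIN-V arm or, with a zero placebo rate, at the whole trial. The gap is wider at 2% (0.55 against 0.70). An added row and a reworded example would cost almost nothing.

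The arithmetic stands, and so does the observation that no section prints the N = 40 figures. The claim that the table misleads is weaker:

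- The denominator is stated in the sentence that introduces the table, and the arm sizes are in the section just before.
- Pooling suits the setting. Relatedness is judged by blinded staff, and the halting rules count participants without regard to arm. Under section 5.3.2 the DSMB may see data by group with the groups unidentified.
- Section 3.4.1 covers the applicator as well as the product, and section 6.1 gives placebo women an identical applicator, so applicator events can arise in all 60.
- Sections 2.4 and 2.6.1.1 report AEs spread evenly between arms in earlier trials. A zero placebo rate is one scenario among several.
- Section 11.5 does not state a denominator for its exact intervals. Intervals by arm are the natural reading, because the sentence follows a summary by arm. On that reading the results will carry the precision of each arm's own size, whatever the planning table shows.

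**Conclusion.** The concern does not call for a change. The table is correct for what it says it covers: all 60 participants, at a true rate averaged over them. It makes no promise about the LACTIN-V arm. The missing companion figures for 40 women are 0.18, 0.33, 0.55 and 0.87 at 0.5%, 1%, 2% and 5%. They follow in one line from the arm size in section 11.3, and a statistician briefing the DSMB would supply them if asked.

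An extra row would be harmless, but it would alter no sample size, halting rule, analysis or conclusion. This is a gap in detail that analysts fill sensibly, alongside a trivial slip in a row label.

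The figures assume that all 40 LACTIN-V women are followed; dropout would lower the N = 40 values, and losses in either arm would lower the pooled ones. The conclusion does not depend on that assumption. It rests on the stated denominator, the reproduced entries, and the absence of any decision driven by the table.

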# 11.5. Statistical Analysis Plan

The primary analyses in Objective 1 is to compare the levels of i) pro-inflammatory genital tract cytokines levels & proportion of subjects with a significant decrease ( $\geq 1 \log_{10}$ ) in cytokines levels, ii) HIV target cells (i.e., CD4+/CCR5+/HLA-DR+/CD38+ T cells) and iii) anti-HIV effect of CVL, as assessed by HIV p24 levels, between the two treatment arms.

Graphical and descriptive measures (such as frequency, percent mean, median, standard deviation and IQR) will be used to summarize data. Spearman rank correlation will be used to examine associations among the aforementioned outcomes. Statistical tests (such as the two sample T and Wilcoxon rank sum tests) will be used to compare levels of cytokines, HIV p24 levels and HIV target cells between the two treatment groups.

For within group comparison, statistical tests (such as paired T and Wilcoxon signed rank tests) will be used. Longitudinal data analyses using nonlinear mixed models or generalized estimating equations will be performed to examine and compare the overtime changes in cytokines levels and HIV target cells. Fisher's exact test will be used to compare the proportion of subjects with a significant decrease ( $\geq 1 \log_{10}$ ) in cytokines levels.

Data classification and dimension reduction techniques (e.g., principal component analysis, and cluster analysis) will be used to group a set of cytokines or HIV target cells to uncorrelated summary variables or to identify study subjects with similar cytokine or HIV target cell profiles. Adjustment will be made for multiple comparisons using less conservative multiple testing correction procedures (such as the Holm's and Benjamini-Hochberg methods) where appropriate.

The primary analysis in Objective 2 is to compare the presence and abundance of *Lactobacillus spp*. (including *L. crispatus* CTV-05) between the two study groups. As in Objective 1, graphical and descriptive measures will be used to summarize data. Fisher's exact test will be used to compare presence of specific strains of vaginal lactobacilli and cervicotypes (CT). Empirical Bayes method will be used for identification of microbes that show differential abundance between study arms. Empirical Bayes method is more efficient due to its ability of pooling information across microbes.

Sparse clustering, where clustering and feature selection are integrated, will be used to identify study subjects with similar microbial profiles. Sparse clustering has a number of advantages. If the underlying groups differ only in terms of some of the features, then it might result in more accurate identification of these groups than standard clustering. It also yields interpretable results, since one can determine precisely which features are responsible for the observed differences between the groups or clusters. Similarly, Sparse Principal Component analysis will be used to group a set of highly correlated microbial reads to uncorrelated summary variables. As in Objective 1, adjustment for multiple testing will be made using less conservative multiple testing correction methods (e.g., Benjamini-Hochberg).

Solicited AEs will be analyzed by taking the most severe response over the Day 64 followup period. The analyses of AEs and SAEs is mainly descriptive. Descriptive measures (frequency and percent) will be used to summarize the proportion of participants with product-related AEs (Grade 0, Grade 1, Grade 2, and Grade 3) in each treatment arm. Confidence intervals for AEs rates will be estimated using methods for exact binomial confidence intervals. Fisher's exact test will be used to compare rates of AEs between the two treatment arms. Multivariate analyses using logistic regression models will be used to compare AEs rates between the two arms while adjusting for the effect of other covariates.

Unsolicited AEs will be coded by MedDRA® for preferred term and system organ class. The proportion of participants and exact 95% confidence intervals of AEs in aggregate, as well as by MedDRA® categories, will be computed. The number of SAEs will be reported by a detailed listing showing the type, MedDRA® coding, relevant dates (treatment dosing dates and AE onset and resolution dates), severity, relatedness, and outcome for each event.

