## 4.0 STUDY DESIGN

This is a Phase 2 randomized double-blind placebo-controlled trial to assess the impact of the live biotherapeutic product LACTIN-V containing *Lactobacillus crispatus* CTV-05 on the vaginal microbiome of young women in South Africa at high risk of HIV acquisition.

The study will also assess the safety of LACTIN-V by comparing the incidence of AEs between women randomized to LACTIN-V or placebo.

We will conduct a randomized, placebo-controlled trial of LACTIN-V in a cohort of young South African women with a non-*Lactobacillus* dominant microbiota, who are sexually experienced, age 18 to 23 years. Enrolment will be continued until 60 women will be randomized into the study.

Eligible women will be treated with oral metronidazole 400 mg twice daily for seven days and will then be randomized 2:1 to LACTIN-V vs. placebo.

Within 8-48 hours of taking the final metronidazole dose, women will receive the study product for five consecutive days, followed by a twice weekly dose for three additional weeks.

After enrolment and metronidazole treatment, women will be followed throughout the 4 weeks of dosing and the 4 weeks of post-dosing phase for a total of 10 weeks (until approximately Day 64).

The primary outcome (**Objective 1**) focuses on the ability of the *L. crispatus* CTV-05 to acutely decrease genital tract inflammation (as a marker of HIV susceptibility). This will be assessed by collecting cervicovaginal fluid and endocervical immune cells at randomization (Day 8), after 4 weeks of treatment with the LACTIN-V vs. placebo (Day 36), and after 4 weeks of post-dosing phase (Day 64).

Direct anti-HIV activity will be assessed with *in vitro* HIV infection assays using vaginal fluid samples from randomization and after treatment: Randomization Visit (Day 8), Follow-up Visit (Day 36), and Final Visit at Day 64.

A secondary outcome (**Objective 2**) is to assess the ability of the *L. crispatus* CTV-05 to establish durable vaginal colonization as with the potential as a self-sustaining prevention strategy. This will be assessed by characterization of the vaginal microbiome at the baseline FRESH Study Visit, and the end of treatment (Day 36) and at the Final Visit (Day 64), after 4 additional weeks during the post-treatment phase.

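### The Section 11.5 between-arm tests of cytokine, p24 and HIV-target-cell levels name no baseline covariate, although Day 8 pre-dose values are collected for all three

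*Combined protocol and SAP*

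**What the plan says.** Section 11.5 gives the level comparisons primary status: "The primary analyses in Objective 1 is to compare the levels of i) pro-inflammatory genital tract cytokines levels & proportion of subjects" reaching the response threshold, followed by HIV target cells and the anti-HIV effect of lavage fluid measured by p24. The between-arm method is: "Statistical tests (such as the two sample T and Wilcoxon rank sum tests) will be used to compare levels of cytokines, HIV p24 levels" and target cells. No covariate is named, and the text does not say whether the tested value is the follow-up level or the change from baseline.

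The same section adds: "Longitudinal data analyses using nonlinear mixed models or generalized estimating equations will be performed to examine and compare the overtime changes" in cytokines and HIV target cells. It does not list p24 there. It does not state which visits enter, how baseline is handled, or whether these models or the two-sample tests lead. The responder proportion is compared with Fisher's exact test.

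Pre-dose values exist. Section 4.0 collects cervicovaginal fluid and endocervical cells at Day 8, and plans the anti-HIV assays "using vaginal fluid samples from randomization and after treatment: Randomization Visit (Day 8), Follow-up Visit (Day 36), and Final Visit at Day 64". Section 7.3 places the Day 8 pelvic sampling before randomisation and the first dose. Section 11.2 takes the FRESH visit as the cytokine baseline, while Section 3.4.1 refers to both visits. The arms are "n=20 for the placebo arm A and n=40 for the LACTIN-V arm B" (Section 11.3).

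**The concern.** A two-sample t or rank sum test on follow-up levels leaves all between-woman variation that baseline could explain in the error term. With only 20 women on placebo, the arms can also start apart by chance, and an unadjusted test carries part of that gap into the Day 36 difference. These comparisons supply the mechanistic evidence for Objective 1, and the data needed to adjust them are already being collected.

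Because the lead analysis is not named, a baseline-using model and an unadjusted test of the same measure could disagree with nothing in the plan to settle which counts. For p24 there is no baseline-using between-arm analysis to fall back on.

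**Working it through.** **The plan's own figure.** Section 11.3 states more than 88% power for 10% v 50% responders at 20 v 40, two-sided Fisher's exact test at 5%. Summing exactly over Binomial(20, 0.10) × Binomial(40, 0.50) gives 89.1%, so the figure reproduces. That endpoint, a fall of at least 1 log10 "in at least 3 of 9 proinflammatory cytokines in CVL specimens on the Day 36 Visit", is defined from each woman's own baseline and is not touched by what follows.

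**Inputs for the level comparisons.** Arm sizes 20 and 40 come from Section 11.3. The documents give no SD, no target difference in levels and no correlation. The following are therefore assumed: an effect of 0.7 SD, baseline to Day 36 correlation r from 0.1 to 0.7, two-sided 5%, and no dropout.

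**Formulas, in SD units.**
- Standard error of a mean difference: SE = √(1/20 + 1/40) = 0.274.
- Follow-up-only t-test: noncentrality 0.7/0.274 = 2.556 on 58 df, power 71.0%.
- ANCOVA: residual SD √(1 − r²), so noncentrality 2.556/√(1 − r²) on 57 df.
- Equivalent unadjusted sample size: 60/(1 − r²).
- Imbalance: the baseline mean difference has SD 0.274, so P(|difference| > 0.5) = 2[1 − Φ(0.5/0.274)] = 2[1 − Φ(1.826)] = 6.8%.
- Type I error of the unadjusted test given a 0.5 SD baseline difference: the Day 36 difference is centred at 0.5r with SD √(1 − r²) × 0.274, and the rejection limits are ±1.96 × 0.274 = ±0.537.

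| r | Unadjusted power | ANCOVA power | Equivalent unadjusted N | Type I error given 0.5 SD imbalance |
|---|---|---|---|---|
| 0.1 | 71.0% | 71.4% | 61 | 5.3% |
| 0.2 | 71.0% | 72.7% | 62.5 | 6.1% |
| 0.3 | 71.0% | 75.0% | 66 | 7.4% |
| 0.5 | 71.0% | 82.7% | 80 | 11.4% |
| 0.7 | 71.0% | 94.0% | 118 | 17.0% |

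As an example of the last column, at r = 0.5 the shift is 0.25 and the conditional SD is 0.237. The upper tail is 1 − Φ((0.537 − 0.25)/0.237) = 1 − Φ(1.21), about 11.4%, and the lower tail is negligible.

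**Checks.** An effect of 0.78 SD gives the unadjusted t-test 80% power. There the ANCOVA formula gives 83.5%, 89.9% and 97.5% at r = 0.3, 0.5 and 0.7. Simulation (8,000 trials per setting) gives 82.6%, 88.9% and 97.2%, so the formula is optimistic by at most about one point. Under the null, the simulated overall type I error of the unadjusted t-test is 4.8% to 5.4%. At a milder imbalance of 0.25 SD its conditional error is 4.8%, 4.4% and 3.2% at r = 0.3, 0.5 and 0.7. Low values of this kind offset the high ones, which is why the overall rate is nominal.

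**If levels means change from baseline.** A change-score t-test has SD √(2(1 − r)). At 0.78 SD its power is 65.8%, 80.0% and 95.1% at r = 0.3, 0.5 and 0.7, against 80% for follow-up only. It is worse below r = 0.5, equal at 0.5, and below ANCOVA throughout. The alternative reading does not remove the point.

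**The case against.** The strongest reply is that Section 11.5 does use baseline. It plans longitudinal models of change for cytokines and target cells and a Fisher test on a decrease, and Section 11.2 states the cytokine and target-cell outcomes relative to baseline. A reader might infer that the plan ignores pre-randomisation values; for those two measures the documents do not support that. What stands is that the model is unspecified and unranked, and that p24 is left out of it.

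Second, the correlation is unknown and could be low. The FRESH sample may be taken 30 days before enrolment, hence about 30 + 35 = 65 days before Day 36, with a metronidazole course in between; Day 8 is sampled 8 to 48 hours after that course ends. This is fair. At r of 0.2 or less the power gain is under 2 points. It argues for modest claims, not against adjusting, since the price is one degree of freedom.

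Third, a reader might infer that the unadjusted tests inflate type I error. They do not overall. The 5% to 17% applies only to a trial that happens to show a 0.5 SD imbalance.

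Fourth, one might call GEE invalid at this size. Section 11.5 names no variance estimator, so only the missing specification can be criticised. The word nonlinear is likewise used with no mean curve defined.

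**Conclusion.** The point holds as a matter of efficiency and prespecification. The named between-arm tests of levels carry no baseline covariate, the longitudinal model does not say how baseline enters or which analysis leads, and p24 has no named between-arm analysis that uses baseline.

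At 20 v 40 and an assumed 0.7 SD effect, adjustment raises power from 71% to between 71% and 94% for correlations of 0.1 to 0.7. The gain cannot be narrowed further from the documents. A baseline difference above 0.5 SD is expected in about 7% of trials for any one measure. It would be wrong to read this as undermining the trial's stated power: that belongs to the Fisher responder test, which reproduces and stands.

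**What to change.** In Section 11.5:

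- Make the lead between-arm comparison of levels at Day 36 (and Day 64) an ANCOVA on the log10 scale, with arm and the woman's own Day 8 pre-dose value, for each cytokine, target cells and p24.
- Add a rank-based ANCOVA as a sensitivity analysis to deal with zeros and values below detection.
- Name Day 8 as the covariate visit. The FRESH value may be a second covariate for cytokines if this is prespecified.
- Specify the longitudinal analysis as a linear mixed model with visit as a factor and small-sample degrees of freedom, or as GEE with a bias-corrected variance. Include p24.
- Keep Fisher's exact test on the responder endpoint as the powered analysis.

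The cost is one degree of freedom per comparison and SAP wording. No new samples, visits or women are needed.
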